3. STUDY DESIGN

Type of Trial

This is a double blind randomised placebo controlled trial. We anticipate an 18 month period from first Participant recruitment, with a further 6 months for outcome ascertainment, analysis and reporting (see Figure 1, Appendix 3: study timeline for further details). Each participant will be asked to administer the intervention (pravastatin or placebo) for a total of 7 days or until delivery (whichever occurs soonest), and will be followed up until 28 days after the estimated date of delivery (EDD).

Potential participants for recruitment will be identified following presentation to acute obstetrics services with threatened preterm labour. Women at high risk of preterm labour and delivery will also be identified from Antenatal Clinics i.e. the Preterm Birth Clinic (if available locally) and provided with information regarding the trial. Should these women then develop signs and symptoms of preterm labour, it is hoped that pre-information about the trial will improve recruitment.

Duration of trial

The primary outcome (recruitment) will be measured from the first participant's first visit to 28 days post EDD of the last (40th) participant's (recorded as last participant's last visit). Monitoring of secondary outcomes will begin following consent of the first participant to EDD plus 28 days of the last participant recruited.

Treatment Phase

The total treatment phase will be 7 days for each participant, or until delivery (whichever occurs soonest). Follow up will continue until EDD + 28 days.

Outcome Measurement

On recruitment to the trial, all participants will receive a study diary. They will record adverse events, compliance with treatment and administration and exact timing of self-medication with the IMP. Contraction frequency will also be recorded, either as monitored by the clinical team caring for the participant, or the participant herself. These data will be collected daily by the participant for the duration of the intervention (7 days or until delivery, whichever occurs soonest). Diaries will be collected at the day 7 visit by the research team member conducting the visit, and transcribed to pCRF and/or eCRF. Other outcomes will be reviewed and collected from the participant's clinical medical notes.

Feedback Questionnaire

At, or close to, EDD + 28 days, feedback regarding the participants' experiences of PIPIN will be requested in the form of an itemised questionnaire with space for free-text comments. Participants will be contacted via their preferred method of contact (telephone, email or post). Should the conversation be via telephone, responses provided will be recorded by a member of the research team on the form.

Should participants express concern regarding their care, these concerns will be explored. Participants will be offered the opportunity of raising their concerns either formally, or informally, with a senior member of the research team. They can also be directed to the senior clinician responsible for their care, or to the formal NHS Lothian complaints team. Details of this are included in the PIL.

Location of trial visits

Should participants remain in hospital for the duration of the treatment phase, but not progress to delivery, all trial visits will occur in the inpatient setting.

CR007-T01 v4.0 PIPIN Protocol Version 5.0 17/05/2019 Page **15** of **45**

For participants discharged to the community during the treatment phase by their obstetrician, a mutually convenient appointment will be made for the day 7 trial visit. This may occur in hospital or at the participants' home depending on their availability.

Blood Tests

All participants will have baseline LFTs and CK, a twice daily inflammatory profile (see 2.2.2 for details) on day 1, a single inflammatory profile on day 2, and a further inflammatory profile + LFTs/CK at the day 7 trial visit. Serum pravastatin level will also be checked at baseline, and concomitantly with all inflammatory profile measures for compliance assessment.

At the time of delivery, all participants will have serum and cord samples taken for an inflammatory profile as above, and, for those who deliver within the 7 day treatment phase, a serum and cord pravastatin level

A summary of these blood tests can be found in appendix 3, and exact methods for sampling, storage and processing will be detailed in a separate document.

Contraction Frequency

For participants who are contracting at a frequency \geq 1 in 10 minutes post randomisation, uterine contraction frequency will be recorded every hour until delivery, or until contractions occur at a frequency of <1 in 10 for 4 consecutive hours. Participants will be shown how to monitor contraction frequency and will record this in their diary.

Compliance

Compliance (number of tablets taken) will be collected from the participants' medical records and at the day 7 trial visit (from the participant's diary) and the returned medication bottles. Serum pravastatin levels will also be taken to evaluate compliance.

Timing from presentation to first dose administered

Timing of presentation to first treatment dose administered will be collected from the participants' medical records.

Delivery, post-natal and neonatal outcomes

At the time of delivery, secondary outcomes of gestational age at delivery, markers of fetal and maternal inflammation and pravastatin levels will be collected (via medical records and maternal and cord blood samples).

Maternal and neonatal outcomes will be monitored and information extracted from the participants medical records until EDD + 28 days.

Acceptability of the Trial

This will be collected at two points:

- 1) Percentage uptake of eligible participants to the trial
- 2) At or near 28 days post EDD, participants will be contacted using their preferred method of contact, thanked for their involvement and asked for feedback.

Stopping Rules

We have set the following safety rules for PIPIN based on maternal and neonatal deaths that are possibly or definitely related to IMP. We have based these rules on the expected frequency of maternal and neonatal deaths in the population.

CR007-T01 v4.0 PIPIN Protocol Version 5.0 17/05/2019 Page **16** of **45**

We do not anticipate that there will be any maternal deaths (maternal death rate in the UK is 8.5 per 100,000). So in n=40 women we would not expect any deaths – we would need to recruit almost 12,000 women to expect 1 death.

We anticipate that the death rate of babies in the PIPIN population will be at least 6% (based on the Oracle study, which also recruited women in preterm labour (Kenyon et al. 2001). The Oracle study recruited women suspected clinically to be in preterm labour; in PIPIN we will recruit women in whom a "test" has additionally confirmed the onset of preterm labour, hence preterm birth (with associated neonatal death) is more likely to occur in PIPIN).

With an expected death rate of 6%, we consider that a doubling of this rate would be grounds for serious concern, if such deaths were thought to be related or possibly related to study IMP, that will prompt a halt in recruitment pending review by the independent DMC (iDMC), We will randomize around 20 to pravastatin, and assume there is no cross over from placebo to pravastatin (although of course as safety data these will be analysed according to treatment received). If there is 1 death thought to be related to IMP in any the first 10 randomised to pravastatin, or cumulatively 2 deaths in the first 20 randomised to pravastatin, this will trigger a review by the iDMC, and if the iDMC believes that it is plausible that the deaths are related to the IMP, the DMC will advise whether the trial should be stopped, or the circumstances under which the trial should continue.

The two most severe class side effects of statins, that is liver toxicity (defined by jaundice, hepatitis or fulminant hepatic necrosis) and muscular toxicity (rhabdomyolysis), both occur at a frequency of less than 1 < 10,000. Occurrence of these in any participant with reasonable suspicion of causation due to the IMP will prompt review of unblinded data by the DMC.

4. STUDY POPULATION

4.1 NUMBER OF PARTICIPANTS

We will to recruit 40 participants. Eligible participants are pregnant women presenting in preterm labour at 24+0 to 35+6 weeks gestation. Preterm labour is defined as regular uterine activity with either a positive fetal fibronectin (See Appendix 5) or evidence of cervical change as monitored through cervical length scanning or direct observation of dilation.

We estimate a duration of 2 years with an 18 month recruitment period. Follow up of participants to last Participant last visit will take up to another 6 months.

4.2 INCLUSION CRITERIA

To be eligible to take part in the PIPIN study, the below inclusion criteria must be met:

- Ability to Give Consent
- Gestation ≥24+0 and ≤ 35+6 weeks (based on dating scan obtained at ≤ 16 weeks gestation)
- Singleton pregnancy
- Aged 16 years or above
- Not previously recruited to this study in this pregnancy
- Intact membranes
- A positive fetal fibronectin test (See Appendix 5) OR a short cervical length (≤ 15mm) on ultrasound examination OR cervical dilation ≥ 3cm and less than fully dilated
- Uterine activity defined as ≥ 1 palpable contraction over 20 minutes of CTG monitoring.

CR007-T01 v4.0 PIPIN Protocol Version 5.0 17/05/2019 Page **17** of **45**

- No major congenital anomalies evident on the 20 week anomaly scan, or any further anomaly scans performed subsequently. If an anomaly is present, this should be classified as per ICD-10 codes and minor anomalies discussed for inclusion on a case by case approach involving the clinical team, the PI and the participant.
- Not demonstrating any of the exclusion criteria as detailed below

4.3 EXCLUSION CRITERIA

- Immediate delivery deemed necessary for fetal or maternal reasons as determined by a senior clinician.
- Pre-labour, preterm rupture of membranes in the index pregnancy
- Obstetric Cholestasis as defined by RCOG (RCOG Green-Top Guideline, Number 43)
- Established severe pre-eclampsia or HELLP syndrome as defined by NICE guidance (Hypertension in pregnancy: diagnosis and management | Guidance and guidelines | NICE n.d.)
- Known History of hepatic or renal impairment
- Ingestion of drugs thought to alter the pharmacokinetics or efficacy of statins, including erythromycin and/or nifedipine.
- Taking any one of the prohibited drugs as listed the SmPC and in 6.7.3
- Lactose intolerance (due to excipient in Pravastatin and placebo)
- Current or previous alcohol misuse
- Personal or first degree relative with heritable muscle disorders
- Participating in another CTIMP trial

4.4 CO-ENROLMENT

Patients already recruited to a non-CTIMP trial will be permitted to co-enrol as per the ACCORD Co-enrolment Guidelines (GL001 Guidelines for Co-enrolment).

Patients already recruited to a CTIMP will not be eligible. This will be checked for by direct questioning of the patient and review of the patient's electronic health record.

5. PARTICIPANT SELECTION AND ENROLMENT

5.1 IDENTIFYING PARTICIPANTS

Two strategies of participant identification will be used. Those at high risk of preterm labour and delivery are routinely seen at a dedicated antenatal clinic, and during these visits will be offered an invitation letter by a member of their clinical care team. This letter will contain information about the trial. They will also be offered the opportunity to discuss the trial with their clinical team and the research team. This should improve participant understanding should they subsequently present acutely with preterm labour, and may improve recruitment.

Secondly, eligible participants will be identified by their clinical care team on presentation for acute assessment or care with signs and symptoms of preterm labour. Participants will be offered a PIL and the opportunity to discuss the trial, and should they wish to proceed, delegated clinical care providers will be able to assess for eligibility and consent participants.

CR007-T01 v4.0 PIPIN Protocol Version 5.0 17/05/2019 Page **18** of **45**

Should participants require additional investigations to confirm eligibility e.g. a cervical length scan (in the case of contraindication to fetal fibronectin for example), this can be arranged through the scanning department or by contacting the trial team. Should participants be identified as appropriate by the clinical team and happy to discuss the trial, but no delegated personnel available for consent, the trial team can be contacted to attend.

5.2 CONSENTING PARTICIPANTS

Participants will be offered PIL by a member of their clinical care team at the time of presentation for acute assessment and care, and an appropriate amount of time allowed for consideration of participation. Whilst the nature of the intervention is time-critical, they will of course be offered as long as required to consider participation.

Both obstetric and midwifery staff who have completed the appropriate training will be delegated to consent participants.

Potential participants who may not adequately understand written or verbal information in English, an approved translator will be offered. Where this is not possible in a timely fashion, the NHS-approved telephone interpretation service will be offered. Signing interpreters will be offered where required and if available. For participants with a visual impairment, both the PIL and consent form can be verbally read to them, and completed in the presence of a witness.

5.3 SCREENING FOR ELIGIBILITY

Pre-randomisation assessments to confirm eligibility include one or more of the following:

- A positive fetal fibronectin (See Appendix 5), obtained in accordance with hospital guidelines.
 - Clinically confirmed cervical dilation \geq 3cm
 - A cervical length < 15mm. (In the case of patients who have had multiple LLETZ procedures, and are known to have a shorter cervix from serial assessments, those with a > 50% reduction compared with a baseline length will also be eligible).

Eligibility will be confirmed by appropriately trained, delegated clinicians and confirmation of this recorded in the participants' medical records.

An anonymised screening log will be maintained of all patients considered for the trial, including those who decline to participate. This will include patient age and gestation at presentation, as well as the results of the above screening tests.

If a participant declines to participate, withdraws prior to randomisation, or is excluded following consent but prior to randomisation for any reason, the minimal anonymised information will remain on the screening log. If participants are willing to offer a reason for declining to participant, this will also be held on the screening log.

5.4 INELIGIBLE AND NON-RECRUITED PARTICIPANTS

Details will be maintained as above for ineligible participants including reason for ineligibility, and these patients will be treated as per local guidelines for preterm labour.

For participants who consent to participation but who are not randomised, reason for this will be recorded in the screening log e.g. Participant withdrew consent or delivered prior to administration of first dose of intervention. This is an intention to treat study therefore data will be collected from consented, non-randomised participants.

CR007-T01 v4.0 PIPIN Protocol Version 5.0 17/05/2019 Page **19** of **45**

5.5 RANDOMISATION

5.5.1 Randomisation Procedures

Participants will be randomised to active or placebo in a 1:1 ratio. Randomisation block size will use permuted blocks of size 2, 4, and 6, randomly sorted, and spliced with occasional randomly inserted simple runs of random length to aid unpredictability. Randomisation codes will be provided to ISG by ECTU, and packs dispensed in a sequential fashion from these. Details of the study pack number allocated will be recorded in the Participant's notes, on the medication record as well as in the drug accountability log in the treatment room of labour ward.

This trial will be double blinded. Randomisation codes will be held by both ECTU and the local Pharmacy department.

5.5.2 Treatment Allocation

Drug stocks will be held by the local pharmacy department with a small supply located in a locked cupboard in the clinical treatment area i.e. Labour Ward. Following randomisation, the next sequential pack as allocated will be detailed in the accountability log and removed from the clinical treatment area supply shelf, checked out with the consenting physician and an additional member of staff, and prescribed on the inpatient drug Kardex as 'study drug pravastatin/placebo code *** 1 tablet every 24 hours.' Following dispensing, the first dose will be administered to the participant in a timely fashion.

Whilst as an inpatient, the trial drug can be dispensed either by the midwife caring for the participant as with standard prescribed medication, or by the participant herself (marked as 'self' on the Kardex). The box containing the trial drug can be stored in the locked bedside cabinet to avoid loss / missed doses. Participants will receive instructions to take one tablet each day, at the same time each day.

Administration of the drug will be discontinued after 7 days (i.e. 7 doses) of treatment or following delivery if sooner.

Should the participant be discharged prior to completion of the 7 day course, the trial medication will be prescribed on the discharge letter under 'other drug' and using the same terminology as on the medication Kardex (including pack number). The participant will be advised to continue taking the medication once daily until there are no further tablets remaining.

There will be space in the participants' daily diary to record the time of dose administration.

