5.6 WITHDRAWAL OF STUDY PARTICIPANTS

Participants are free to withdraw from the study at any point or a participant can be withdrawn by the Investigator. Pre-specified investigator initiated indications for study withdrawal includes:

- Consent withdrawn
- SUSAR
- Fetal demise in utero
- If the participant develops severe pre-eclampsia or HELLP syndrome
- The clinical team judge that immediate delivery is advised, for example in the case of development of severe sepsis or evidence of fetal compromise.

Note that delivery is not a reason for withdrawal as this is an outcome.

If withdrawal occurs, the primary reason for withdrawal will be documented in the participant's medical records and CRF if possible. The participant will have the option of withdrawal from:

- (i) Taking the study medication, with continued study procedures and collection of clinical and safety data
- (ii) all aspects of the trial but continued use of data collected up to that point

If a participant wishes to withdraw from the trial, the trial team will be informed and withdrawal will be recorded in the medical notes, along with the aspects from which they wish to withdraw.

Participants that withdraw following administration of the first dose of intervention or any doses thereafter will not be replaced. Data will continue to be collected where possible to allow intention to treat analysis.

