6. INVESTIGATIONAL MEDICINAL PRODUCT AND PLACEBO

6.1 STUDY DRUG

6.1.1 Study Drug Identification

Pravastatin Sodium 40mg tablets

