14.7 CONTINUATION OF DRUG FOLLOWING THE END OF STUDY

When the participant delivers her infant or completes 7 days of treatment (whichever occurs soonest), the drug will stop being administered.

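### The discharge advice in section 5.5.2 omits the stop at delivery that the protocol sets everywhere else

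*Protocol*

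**What the plan says.** Section 5.5.2 (Treatment Allocation) first gives the general rule: "Administration of the drug will be discontinued after 7 days (i.e. 7 doses) of treatment or following delivery if sooner". The next paragraph covers women discharged before the course is complete. The drug goes on the discharge letter in the wording used on the inpatient chart, and "The participant will be advised to continue taking the medication once daily until there are no further tablets remaining". The chart entry gives the frequency as "1 tablet every 24 hours".

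Two other places set the end of treatment. Section 3 (Study Design) defines the treatment phase as 7 days or until delivery, and words it as a request to every woman: "Each participant will be asked to administer the intervention (pravastatin or placebo) for a total of 7 days or until delivery (whichever occurs soonest"). Section 14.7 says: "When the participant delivers her infant or completes 7 days of treatment (whichever occurs soonest), the drug will stop being administered".

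The rest bears on supply and return. Section 6.1.4 provides bottles of 7 doses. Section 6.1.1 identifies the product as "Pravastatin Sodium 40mg tablets". Section 6.3 has participants dispense to themselves after the first dose, for a total of 7 days, and does not mention delivery. Section 6.1.7 has the bottle collected and the contents counted at the day 7 visit.

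**The concern.** The drug is given to prolong pregnancy, so a capsule taken after the birth serves no trial purpose and is exposure beyond the protocol's own limit. In hospital, staff see each dose and can stop it. At home the woman controls the dosing, so the advice she is given on leaving matters. Section 5.5.2 specifies that advice in one sentence, and the sentence ties the end of dosing to the empty bottle.

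Compliance is a secondary endpoint, and section 6.5 measures it partly by counting what remains in the bottle. If a woman delivers on day 3 and returns an empty bottle at day 7, she has followed the discharge advice and broken the stop rule. The count alone does not show which doses came before delivery.

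**Working it through.** The plan gives no figure on this point to reproduce. The check sets the two instructions side by side and then counts capsules.

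**Do the instructions differ?**

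- She has not delivered by day 7 and has missed no dose. The stop rule gives 7 doses. The discharge advice empties a 7-dose bottle, so it also gives 7 doses. They agree.
- She goes home and delivers after *d* doses, with *d* from 1 to 6. The stop rule gives 0 further doses. The discharge advice gives 7 − *d*. They differ.
- She has not delivered and has missed *m* doses. The limit in sections 3 and 14.7 is 7 days. At one capsule a day the bottle lasts until day 7 + *m*. They differ by *m* days, unless the bottle is collected on time at day 7.

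**Size of the difference at delivery**

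Inputs: 7 doses per bottle (section 6.1.4) and 40 mg per dose (section 6.1.1), so a full course is 7 × 40 = 280 mg.

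Formulas: capsules left = 7 − *d*; pravastatin left = 40 × (7 − *d*) mg; share of course = (7 − *d*)/7.

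| Doses taken before delivery | Capsules left | Pravastatin arm, mg | Share of course | Allowed by stop rule |
|---|---|---|---|---|
| 1 | 6 | 240 | 86% | 0 |
| 2 | 5 | 200 | 71% | 0 |
| 3 | 4 | 160 | 57% | 0 |
| 4 | 3 | 120 | 43% | 0 |
| 5 | 2 | 80 | 29% | 0 |
| 6 | 1 | 40 | 14% | 0 |

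These are ceilings. They assume that no dose was missed, that the advice is followed to the letter, and that nobody tells her to stop. A day 7 visit held on time and before the seventh dose removes at most one capsule from each row (7 − 6 = 1). Women in the placebo arm would take the same number of capsules without pravastatin.

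**How many women?** The protocol gives no rate of discharge followed by delivery within 7 days, so no expected count can be derived.

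**The case against.** The best defence is that the rule stands in the paragraph directly above and is general. Because the bottle holds exactly 7 doses, finishing it can be read as another way of stating the 7-dose limit, in a paragraph that is mainly about continuing supply after discharge. Section 3 addresses every participant, discharged women included, and section 14.7 is flat. Staff at delivery have reason to notice that a woman is still in the treatment phase, because section 7.2 F requires maternal and cord pravastatin levels in that case. The information leaflet, diary and discharge letter are not shown and may already tell her to stop.

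Most of this stands. The intended rule is not in doubt, and a reader might wrongly infer that the protocol has two rival stop rules or means dosing to continue after birth. Sections 3, 5.5.2 and 14.7 rule that out. Three further inferences are also too strong:

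- That delivery keeps the drug going because it does not count as withdrawal. Section 5.6 says "Note that delivery is not a reason for withdrawal as this is an outcome", but treatment ends at delivery through 5.5.2 and 14.7, so withdrawal is not needed.
- That section 7.2 F is at fault for giving no instruction to stop. It is a list of assessments.
- That the letter will carry no duration because it reuses the chart wording. The protocol says how the drug is to be named there, not that an end date is left out.

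The defence does not remove the sentence itself. It states what the woman will be advised, carries no delivery condition, and applies when she is dosing herself. The 7-dose reading does not help a woman who delivers with capsules left, nor one who has missed doses.

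**Conclusion.** The discharge advice in section 5.5.2 is wrong as written, and the point is minor. It omits the stop at delivery that the protocol sets elsewhere. Read literally it allows 1 to 6 capsules (40 to 240 mg in the pravastatin arm) after delivery, and it could take dosing past day 7 after missed doses. The range rests on the 7-dose bottle, the 40 mg dose and literal adherence to that one sentence.

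Only women who leave hospital and then deliver within 7 days, or who miss doses at home, could be affected. That number is not given and is probably small. The primary endpoint, uptake among eligible women, is unaffected. Whether any woman would in fact keep dosing cannot be judged without the leaflet, diary and discharge letter. The documents give no basis for claiming harm to mothers or a distorted comparison of the arms.

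**What to change.** Replace the sentence in section 5.5.2 with: *once daily until delivery or the end of day 7, whichever is sooner, and return any leftover capsules*. Put the same wording in the discharge letter and the diary, if it is not already there. This also settles what happens after missed doses.

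The cost is one sentence in the protocol and matching text in two participant documents. Sample size, visits and analysis do not change. Adding bottle collection to section 7.2 F for deliveries within the treatment phase is optional, since return and counting are already provided for at day 7.
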